6.3 Baseline Assessments

Baseline assessments will be the last assessment prior to the date of the initial application of the study medication. [REDACTED]

[REDACTED]

6.4 Efficacy Variables

The primary efficacy endpoint is the time of complete healing of lesion. Complete healing (defined as loss of crust and re-epithelialization with or without erythema, as assessed by the investigator, based on both clinical observation and review of the subject diary) is measured in days from the time of first dosing. Time-to-complete lesion healing

will also be reported in hours, as a supplemental analysis for informational purposes only. The primary analysis will use time-to-complete lesion healing in days.

[REDACTED]

[REDACTED]

6.4.1 Primary Efficacy Endpoint – Time-to-Complete Healing of Lesions

Time to complete healing of lesions (defined as loss of crust and re-epithelialization with or without erythema, as assessed by the investigator, based on both clinical observation and review of the subject diary) is measured in days/hours from the time of first dosing. The hours will be converted to days for use in the analysis.

Subjects will fall into categories of:

- Complete healing occurred
- Complete healing did not occur

Subject’s report their healing of the lesion in the diary. The investigator reviews the diary to confirm the healing. Complete healing occurs when the subject reported healing with date and time of healing. The subject reported healing time will be used in the analysis.

[REDACTED]

The time until event or censoring will be calculated as described in section 6.2.2.

6.4.2 Other Efficacy Endpoint – Lesion Stages

Lesion stages will be collected via subject diaries. The protocol states lesion stages may include the following categories: stage 0 (no signs), stage 1 (early signs - prodrome), stage 2 (redness), stage 3 (small blister), stage 4 (ulcer), stage 5 (crust) and stage 6 (healed lesion). Stage 0 (no signs) was not collected. The collection of lesion stage was included in the updated version of the diary, so these data are not available for all study subjects.

6.5 Safety Assessments

6.5.1 Extent of Exposure and Compliance to Study Treatment

The extent of exposure to study medication will be quantified for total number of applications applied during the course of the study.

Compliance percentage will be calculated as follows:

$$\text{Compliance} = (\text{total number of applications applied}) / (\text{the number of applications intended during treatment period}) * 100$$

Subjects should apply study medication five (5) times daily for four (4) days. Therefore, the number of applications intended during treatment period is 20.

[REDACTED]

[REDACTED]

6.5.2 Adverse Events

All adverse events (AEs) occurring after signing the informed consent are to be recorded on the AE pages of the eCRF. All AEs will be classified with respect to system organ class and preferred term using MedDRA version 19.0.

6.5.2.1 Definitions

Adverse event (AE)

An adverse event (AE) is any untoward medical occurrence in a subject administered a medicinal product and which does not necessarily have to have a causal relationship with this treatment. An adverse event can therefore be any unfavorable and unintended sign (for example, an abnormal laboratory finding), symptom, or disease temporally associated with the use of a medicinal product, whether or not considered related to this medicinal product.

Serious adverse event (SAE)

Any untoward medical occurrence that meets any of the following criteria:

- Results in death
- Life-threatening event
- Requires in-subject hospitalization or prolongation of existing hospitalization
- Results in persistent or significant disability or incapacity or substantial disruption of the ability to conduct normal life functions
- Results in a congenital abnormality or birth defect
- Any other adverse events that may be considered serious based upon medical judgment

Unexpected adverse event

An unexpected event is any adverse drug experience, the specificity or severity of which is not consistent with the current approved product labeling (package insert) for the study

[REDACTED]

medication, the Investigator's Brochure, or as described in the clinical protocol and consent materials.

Treatment emergent adverse event (TEAE)

Treatment-emergent adverse events (TEAE) are any AEs that occur or worsen (increase in severity and/or frequency) during or after the initial application of the study medication.

For treatment-emergent status regarding events with partial or missing dates, please refer to Section 7.3.

6.5.2.2 Classifications of adverse events assessments

Intensity of adverse events

The maximum intensity of an AE during a day will be recorded on the eCRF. The intensity of an AE will be graded as follows:

- Mild
- Moderate
- Severe

For AEs with unknown or missing severity, a value of "Severe" will be imputed for summary analyses.

Causal Relationship to Study Medication

Causal relationship of AE to study medication will be classified by the Investigator and will be reported as following:

- Definitely related
- Probably related
- Possibly related
- Unlikely related
- Not related

An AE will be considered related to study medication if the relationship is definitely related, probably related, or possibly related. Any missing (unknown or missing) causal relationship of an AE to study medication will be summarized as related.

6.5.3 Clinical Laboratory Evaluations – Urine Pregnancy Test

Females of childbearing potential will have a urine pregnancy test at Visit 1(Screening), Visit 2 (Day 1), Visit 13 (Day 21) and at the End of Study visit.

6.5.4 Other Observations Related to Safety

6.5.4.1 Physical Examination

The physical examination includes ear, nose and throat (ENT), heart, lung and abdomen evaluation, and will be performed at Visit 1 (Screening) and Visit 2 (Day 1).

6.5.4.2 Vital Signs

The vital signs include sitting blood pressure, oral temperature, heart rate, respiratory rate, height and weight, and will be performed at Visit 1 (Screening) and Visit 2 (Day 1).

6.5.4.3 Application Site Reaction Assessment

The application site reaction such as dry lips, desquamation, dryness of skin, cracked lips, burning skin, pruritus, flakiness of skin and stinging of the skin will be assessed as None, Mild, Moderate and Severe at Visit 2 (Day 1) and at each subsequent visit.

Application site reactions will not to be considered as adverse events unless they warrant temporary discontinuation of the study medication, discontinuation from the study or treatment with new concomitant medication.

6.5.4.4 Lesion Symptoms

Lesion symptoms will be collected via subject diaries.

7 STATISTICAL METHODS

7.1 General Methodology

All analysis will be performed after the database is locked and access has been removed from the database and the study treatment codes are unblinded.

All statistical tests will be two-sided with a significance level of $\alpha=0.05$, unless specified otherwise.

Data will be summarized using descriptive statistics (number of subjects [n], mean, standard deviation [SD], median, minimum, and maximum) for continuous variables and frequency and percentage for discrete variables.

For the purpose of display, the summary results will be rounded as follows:

- Min and Max same number of decimals as the raw data.
- Mean and Median one more decimal place than the raw data.
- SD two more decimal places than the raw data.
- Percentages will be displayed with one decimal precision

For categorical variables with missing values, a category documenting the frequency of missing values will be displayed in the summary tables.

Subject listings of all data from the case report forms (eCRFs) as well as any derived variables will be presented.

7.2 Adjustments for Covariates

Not applicable to this study.

7.3 Handling of Dropouts or Missing Data

All available data from subjects who discontinue from the study will be used. Subjects who discontinue the study prior to or after the initiation of the study medication will not be replaced.

For AEs with missing severity, the most severe assessment will be imputed for summary analyses. Any missing causal relationship of an AE to study medication will be summarized as related.

For analyses, partial and completely missing start dates for adverse events and concomitant medications should be imputed as follows:

[Redacted]

[Redacted]	[Redacted]	[Redacted]	[Redacted]	[Redacted]
[Redacted]	[Redacted]	[Redacted]	[Redacted]	[Redacted]

[REDACTED]	[REDACTED]	[REDACTED]	[REDACTED]	[REDACTED]
[REDACTED]	[REDACTED]	[REDACTED]	[REDACTED]	[REDACTED]
[REDACTED]	[REDACTED]	[REDACTED]	[REDACTED]	[REDACTED]
[REDACTED]	[REDACTED]	[REDACTED]	[REDACTED]	[REDACTED]

[REDACTED]

[REDACTED]

- [REDACTED]
- [REDACTED]

[REDACTED]

[REDACTED]

7.4 Interim Analyses and Data Monitoring

No interim analysis is planned for this study.

7.5 Multi-center Studies and Pooling of Centers

Data from all centers will be pooled for descriptive statistics; pooled data will be used for summary tables and descriptive analyses.

For analysis of variance, center will be included as a fixed effect.

[REDACTED]

7.6 Multiple Comparisons/Multiplicity

Not applicable to this study.

7.7 Use of an “Efficacy Subset” of Subjects

The Intent-to-Treat (ITT), Modified Intent-to-Treat (mITT) and Per-Protocol (PP) populations are defined in section 8.3.

7.8 Active-Control Studies Intended to Show Equivalence

The objective of this study is to demonstrate the bioequivalence of Perrigo’s Acyclovir Cream, 5% (Test) to Valeant’s Zovirax[®] Cream 5% (Reference), assessed by mean time-to-complete healing of the lesion. For the purpose of bioequivalence testing, the 90% confidence interval (CI) of the ratio of the means (Test/Reference) must fall within the interval of 0.80 to 1.25.

In addition to testing bioequivalence, the superiority of efficacy of Perrigo’s Acyclovir Cream, 5% (Active) and Valeant’s Zovirax[®] Cream 5% (Active) over Perrigo’s Vehicle of Acyclovir Cream, 5% (Vehicle) will be demonstrated by comparing the mean time-to-complete healing of lesion of the active treatments to that for the vehicle control. Superiority will be considered demonstrated if the means for both active treatments are statistically different from ($p < 0.05$), and smaller than, that for the Vehicle

7.9 Examination of Subgroups

Not applicable to this study.

8 STATISTICAL ANALYSIS

8.1 Disposition of Subjects

The disposition of all subjects who sign an informed consent form (ICF) will be provided. The number of subjects screened and the number of screening failures overall will be presented. The frequencies and percentage of subjects randomized, treated, completed, and discontinued during the study, as well as the reasons for all post-randomization discontinuations, will be summarized by treatment group.

All disposition data will be presented in a subject listing.

Screen failures will not be summarized. A listing of the subjects not meeting the eligibility criteria along with the criteria not met will be presented.

8.2 Protocol Deviations/Violations

Protocol deviations and protocol violations will be evaluated based on the investigators' judgment. These will be identified prior to database lock. The total list of all protocol deviations and protocol violations will be provided to the sponsor after database lock.

[REDACTED]

[REDACTED]

The frequencies and percentages of protocol deviations and protocol violations will be presented by treatment group.

A subject listing will be also be presented for all protocol deviations and violations.

[REDACTED]

8.3 Analysis Populations

Table 5: Population Descriptions

Population	Definition	Displays
Intent-to-Treat (ITT)	Subjects who were randomized, and dispensed the study medication regardless if the medication was used or not by the subject. Subjects will be summarized by randomized (assigned) treatment.	Displays related to subject population, demographics and baseline characteristics, disposition status, medical history, concomitant medication, major protocol deviations etc.
Modified Intent-to-Treat (mITT)	Subjects who met the following criteria will be considered: 
 met Visit 2 inclusion/exclusion criteria; randomized, dispensed and used at least one dose of the study medication; returned for at least one post-screening efficacy assessment. Subjects will be summarized by randomized (assigned) treatment.	The analysis of superiority between active and vehicle will use this population which will be considered the definitive analysis. The bioequivalence of clinical endpoint analysis will be repeated in this population and will be considered as a supportive analysis.
Per-Protocol (PP)	Subjects who met the following criteria will be considered: 
 met Visit 2 inclusion/exclusion criteria; randomized, dispensed and met the protocol criteria for treatment compliance, [REDACTED] had no significant protocol violations that could have interfered with the administration of the treatment or the precise evaluation of treatment efficacy; 
 had Visit 2 investigator assessment within +2 days of first treatment; did not take any prohibited 	The bioequivalence of clinical endpoint analysis will use this population which will be considered the definitive analysis. The analysis of superiority between active and vehicle will be repeated in this population and will be considered as a supportive analysis.

	
medications; - subject-reported healing and had investigator-healing assessment within +2 days of subject-reported healing time
 
Subjects who do not have subject-reported healing, but met the other criteria for PP, can be included in PP population per the following:
 
• [REDACTED]• [REDACTED]• Subjects who did not experience a prodrome, but initiated study treatment, completed the study, and met all the above criteria will be included in the PP population. 
Subjects will be summarized by the actual treatment dispensed.
	
Safety	
Subjects who were randomized, and dispensed the study medication regardless if the medication was used or not by the subject. Subjects will be summarized according to the actual treatment dispensed.
	
The safety displays will use this population which includes (Exposure, AE, application site reaction, physical examinations and vital signs)

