Study Medication:	1. Acyclovir Cream, 5%, Perrigo 2. Zovirax® (Acyclovir) Cream 5%, Valeant Pharmaceuticals 3. Vehicle of Acyclovir Cream, 5%, Perrigo
Study Objectives:	To compare the safety and efficacy profile of Perrigo's Acyclovir Cream, 5% to Zovirax® Cream 5% and to demonstrate the bioequivalence to the reference product as well as superior efficacy of the two active formulations over that of the vehicle in the treatment of herpes labialis (cold sores) in adults and adolescents 12 years of age and older.
Study Design:	Subjects in this multi-center, double-blind, randomized, vehicle-controlled, parallel-group bioequivalence study will be admitted into the study only after written informed consent/assent (as applicable) has been obtained and after all inclusion/exclusion criteria have been met. Male and female subjects, 12 years of age and older, with recurrent herpes simplex labialis will be eligible for enrollment.
Study Population:	██████████ subjects 12 years of age and older, who meet the inclusion/exclusion criteria, will be enrolled.
Dosing:	Subjects will be randomized ██████████ to either the test product, reference product or vehicle treatment group, respectively, and will apply study medication 5 times daily for 4 days. ██████████
Study Visits:	The clinical trial will consist of the following visits: 
• Screening Visit- once the subject meets inclusion/exclusion criteria; they will be randomized and given the study medication. ██████████• Treatment Days: 1 (Visit 2), 2 (Visit 3), 3 (Visit 4), and 4 (Visit 5)• Follow-up Days: 5 (Visit 6), 6 (Visit 7), 7 (Visit 8), 8 (Visit 9), 10 (Visit 10), 12 (Visit 11), 14 (Visit 12), 21 (Visit 13)• ██████████. If healing occurs in-between scheduled study days, the subject should return to the clinic as soon as possible and not wait till the next scheduled visit.

Protocol No: PRG-NY-14-008

Efficacy Assessments:	
The primary efficacy endpoint will be: Time to complete healing of lesions (defined as loss of crust and re-epithelialization with or without erythema, as assessed by the investigator, based on both clinical observation and review of the subject diary), measured in days/hours from the time of first dosing.
 
[REDACTED]

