3.3 Study Design

Screening Visit:

During Visit 1, once the subject meets inclusion-exclusion criteria, they will be randomized and given the study medication. [REDACTED]

Protocol No: PRG-NY-14-008

[REDACTED]

[REDACTED]

[REDACTED]

Treatment Visits:

Subjects will come in for Day 1 (Visit 2) [REDACTED]. At this visit, they will be questioned regarding onset of the episode. The investigator will identify a target area and mark it in the source document.

Clinic visits will take place on Days 2 (Visit 3), 3 (Visit 4) and 4 (Visit 5).

All subjects must be treated with the study medication for 4 days even if the lesion has healed before treatment ends.

Follow-up visits:

The subjects will return their study medication on Day 5 (Visit 6).

Subsequent follow up visits will take place on:

- Days 6 (Visit 7), 7 (Visit 8), 8 (Visit 9), 10 (Visit 10) and 12 (Visit 11).
- Day 14 (Visit 12) will have a window +/- 1 day (i.e. Day 13-15).
- Day 21 (Visit 13) will have a window of +/- 2 days (i.e. Day 19-23).

[REDACTED]

Note:

If the subject's lesion has healed prior to Day 5 (Visit 6), the subject will continue to apply the study medication as proposed for 4 days, and return for all study Visits up to Day 5 (Visit 6), which will be their End of Study Visit.

Protocol No: PRG-NY-14-008

If the lesion is healed after Day 5 (Visit 6) but before Day 21 (Visit 13), the subject will return for their End of Study visit as directed by protocol upon healing and will not have to continue coming to the clinic for the remaining study visits.

[REDACTED]

[REDACTED]

If a subject arrives to the clinic for an unscheduled visit, the subject will go through the same procedures as a scheduled follow-up day. If the subject has not healed by this unscheduled visit, the subject will return to the clinic for the subsequent previously planned follow-up visits.

The use of the study medication should be discontinued after Day 4; however the investigator will continue to monitor the lesion until Day 21 if not healed by then.

[REDACTED]

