5.9.8 Day 21 (Visit 13)

Day 14 (Visit 12) will have a window of +/- 1 day (i.e. Day 13-15).

Day 21 (Visit 13) will have a window of +/- 2 days (i.e. Day 19-23).

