8.4 Measures and Analysis

8.4.1 Efficacy Endpoint and Analysis

The primary efficacy endpoint will be the time to complete healing of lesions (defined as loss of crust and re-epithelialization with or without erythema, as assessed by the investigator, based on both clinical observation and review of the subject diary), measured in days/hours from the time of first dosing.

Equivalence of Clinical Endpoint Analysis

The mean time to complete healing of the lesion for the test and reference treatments will be estimated using analysis of Variance (ANOVA) with treatment and center as fixed effects in the model. The 90% confidence interval for the ratio (Test/Reference) of mean time-to-complete healing will be obtained by Fieller's method. A plot for the ratio (Test/Reference) of mean time-to-complete healing and associated 90% CI will be presented. For the time to complete healing of lesion the Test treatment will be considered to be therapeutically equivalent to the Reference treatment if the calculated 90% confidence interval of the ratio of the means (Test/Reference) falls within the interval of 0.80 to 1.25. Therapeutic equivalent evaluations in the per-protocol (PP) population will be considered the definitive analysis. This analysis will be repeated in the mITT population and will be considered the supportive analysis. Refer to the statistical analysis plan for analysis details.

Analysis of Superiority between active formulation and vehicle

Protocol No: PRG-NY-14-008

For the time to complete healing of the lesion, subjects who received active treatment will be compared to those who received the Vehicle as treatment in order to determine if superior efficacy has been attained.

The time-to-complete healing of both the active products and Vehicle will be analyzed using Analysis of Variance (ANOVA) evaluations with treatment and center as fixed effects in the model.

Each active treatment group will be compared to the Vehicle group using a -two-sided test and tested at an alpha level of 0.05. The mean and its 95% confidence interval will be reported.

Superiority will be considered demonstrated if the means for both active treatments are statistically different from ($p < 0.05$), and smaller than, that for the Vehicle

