8.6.4 Exploratory Analyses

The elapsed time, in hours, between the subject-reported lesion healing date/time and the investigator-assessed lesion healing date/time will be summarized.

The elapsed time is calculated as investigator date/time minus subject date/time.

[REDACTED]

[REDACTED]

[REDACTED]

[REDACTED]

[REDACTED]

[REDACTED]

[REDACTED]

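### Does the +2-day investigator confirmation rule for the per-protocol set bias the definitive equivalence analysis?

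*SAP*

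**What the plan says.** - **The rule.** SAP 8.3, Table 5, admits a subject to PP only with "subject-reported healing and had investigator-healing assessment within +2 days of subject-reported healing time". The exceptions that can be read there are for subjects with no subject-reported healing, or who had no prodrome. Neither helps a subject whose diary time is confirmed late.
- **Role of PP.** SAP 8.3: "The bioequivalence of clinical endpoint analysis will use this population which will be considered the definitive analysis". Protocol 8.4.1 agrees: "Therapeutic equivalent evaluations in the per-protocol (PP) population will be considered the definitive analysis". The mITT repeat is supportive.
- **Value analysed.** SAP 6.4.1: "The subject reported healing time will be used in the analysis". The same section defines the endpoint as healing assessed by the investigator from observation and the diary.
- **Visits.** After Day 1, subjects are seen daily to Day 8, then on Days 10, 12, 14 (window 13–15) and 21 (window 19–23) (Protocol 3.3; SAP 6.2.3, Table 3).
- **Return on healing.** Protocol synopsis: between scheduled days "the subject should return to the clinic as soon as possible and not wait till the next scheduled visit". Protocol 3.3: after Day 5, "the subject will return for their End of Study visit as directed by protocol upon healing". The heading of Protocol 5.9.10 places the healing visit within 24 hours of healing.
- **Delay.** SAP 8.6.4 summarises the lag between diary and investigator: "The elapsed time is calculated as investigator date/time minus subject date/time".

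**The concern.** A late visit does not alter the diary time, yet it removes the subject from the analysis that decides equivalence. Visit spacing is uneven, so the same lapse costs some subjects their place and not others, according to healing time. The plainest case is the week between the Day 14 and Day 21 visits. A subject who heals there and skips the extra visit is next seen more than two days later. Excluding subjects on a post-randomisation outcome can change the Test/Reference ratio of means. If the slower product has more subjects in the trimmed stretch, its mean falls further, the ratio moves toward 1, and a product that is not equivalent could pass more often than 5% of the time.

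**Working it through.** There is no plan figure to reproduce: sample size, SD and expected healing times are redacted. The check has two parts: which healing days are exposed, and what exclusion there does to the ratio.

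**1. Exposed healing days (from the visit schedule)**

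*Unscheduled healing visit missed.* For healing between scheduled days a and b, no assessment falls within +2 days if healing lies in (a, b − 2). This interval is empty unless b − a > 2. On nominal days only 14 to 21 qualifies, giving (14, 19). With the windows:
- narrowest, visits on Days 15 and 19: (15, 17), 2 days;
- widest, visits on Days 13 and 23: (13, 21), 8 days;
- if Visit 12 is held on Day 15, then 15 − 12 = 3, so (12, 13) is exposed too.

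*Scheduled visit missed.* If a scheduled visit falls within 24 hours of healing, it is itself the healing visit. Healing at Day 9.5 with Day 10 missed means the subject is seen on Day 12, and 12 − 9.5 = 2.5 > 2, so the subject is excluded. The same reasoning exposes Days 7–8, 9–10, 11–12, 13–14 and 20–21 (after Day 21 no visit remains). Exposure is therefore not confined to late healers.

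**2. Effect on the ratio (assumed distributions)**

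Assumptions: lognormal times capped at 21 days (unhealed subjects kept at 21); CV 0.4–0.6 before the cap; reference mean 5–8 d and true ratio 1.25, both after the cap; 150–250 per arm; the same non-return fraction p in both arms; no centre effect. For exposed set B:

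PP mean = (E[X] − p·E[X; B]) / (1 − p·P(B))

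At a true ratio of 1.25, false equivalence means the upper 90% Fieller limit falls below 1.25. That is (M_T − 1.25·M_R)/SE < −1.645, with SE² = V_T/n_T + 1.25²·V_R/n_R.

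*One case in full.* Reference mean 7 d, CV 0.5, 200 per arm, p = 0.10, all bands exposed. The assumed distribution gives P(B) = 0.2520 and E[X; B] = 2.556 (Reference), and 0.3673 and 4.087 (Test).
- M_R = (7.000 − 0.2556)/(1 − 0.0252) = 6.919
- M_T = (8.750 − 0.4087)/(1 − 0.0367) = 8.659
- Ratio = 1.252
- V_R = 11.41 with n_R = 195.0; V_T = 16.69 with n_T = 192.7
- SE² = 0.0866 + 0.0915 = 0.1781, so SE = 0.422
- M_T − 1.25·M_R = 0.011, so the probability is Φ(−1.645 − 0.011/0.422) = Φ(−1.671) = 4.7%

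*Ranges, all bands exposed, CV 0.4–0.6:*

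| Non-return | PP ratio (truth 1.25) | False equivalence |
|---|---|---|
| 10% | 1.247–1.255 | 4.2–5.7% |
| 50% | 1.231–1.276 | 2.2–10.9% |

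*Days 14–19 alone, CV 0.5–0.6:*

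| Non-return | PP ratio (truth 1.25) | False equivalence |
|---|---|---|
| 25% | 1.242–1.248 | 5.3–6.6% |
| 50% | 1.234–1.244 | 5.8–8.9% |
| 100% | 1.215–1.234 | 7.4–17.1% |

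With Days 14–19 alone, every shift in the 5–8 d range is toward 1; at a reference mean of 10 d with 100% non-return it reverses (ratio 1.258–1.268). Once all bands are included, the shift goes either way within 5–8 d. If the two products heal alike and non-return is equal, there is no bias.

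**The case for a change.** The strongest case for changing the plan is that PP membership depends on the outcome, in the analysis that decides the trial, while the excluded subject's analysed value is on file. The remedy would be cheap: accept the next attended visit that confirms healing, and keep the strict set as a sensitivity run. The mITT repeat does not isolate this rule, because mITT also lacks the PP compliance and violation criteria. The lag summary in SAP 8.6.4 restores nobody. Unequal non-return would matter even for identical products: in an assumed example with a reference mean of 6–10 d and CV 0.5, 30% against 10% non-return among Days 14–19 healers moves the ratio by about 0.8–2.0%.

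The dependence on healing time is real, and so are the limits of mITT as a check. Three things weigh against acting on them.

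- The endpoint is investigator-assessed. A diary entry that no one verified for a week is a weaker value than one checked within two days, and precise evaluation of efficacy is a stated purpose of the PP criteria. Accepting the next scheduled visit would admit confirmations up to 21 − 14 = 7 days late, or 23 − 13 = 10 days at the window extremes. That exchanges a selection risk for a measurement risk.
- The large figures need half or more of the exposed subjects to ignore a plain instruction to return. No document suggests such a rate, and the blind gives no obvious reason for it to differ between two active creams.
- An added table or sensitivity run would sit beside an mITT repeat that already keeps these subjects, a by-arm summary of protocol deviations and violations (SAP 8.2) and the lag summary. The redacted SAP 8.6.1.2, on exclusion of sites and subjects, may cover the same ground; the conclusion does not depend on that.

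**Conclusion.** The reading of the rule is correct, but no change to the plan follows. Requiring prompt confirmation of an investigator-assessed endpoint is a fair trade-off for a per-protocol set. Its cost is nil if healed subjects return as told. At 10% non-return it is small: false equivalence of 4.2–5.7% against a nominal 5%, with a ratio of 1.247–1.255 where the truth is 1.25. The direction of any shift is not determined, because exposure covers Days 7–8, 9–10, 11–12, 13–14 and 20–21 as well as Days 14–19.

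These sizes rest on assumed lognormal healing times, a reference mean of 5–8 d, CV 0.4–0.6, 150–250 per arm, equal non-return in the arms and unhealed subjects kept at 21 days. The documents that can be read supply none of these. Non-return near 50% would make the effect material (2.2–10.9%). The SAP's lag summary and a comparison of the PP and mITT results would give the analysts an indication of that from data already planned.
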